Patients will be evaluated for disease control rate [complete response (CR), partial response (PR), and stable disease (SD)], or progressive disease (PD) by CT imaging. Contrast enhanced MRI can also be used, as long as the same modality is used throughout the study. Baseline scan results can be accepted from outside institutions, but must be done within 4 weeks of starting therapy and must include (as clinically indicated), chest abdominal, and pelvic CT or MRI. The first response assessment by CT or MRI scans documenting target lesions will be done 6 weeks after first treatment and should be repeated every 6 weeks for the first year, then every 12 weeks thereafter until the end of treatment. If an initial observation of objective response (CR or PR) is made, a confirmation scan should be done at 6 weeks after initial observation. Scans should continue on schedule regardless of delays in ABI-009 dosing.

The efficacy endpoints, DCR (CR, PR and SD), OR (CR + PR), PFS, and RFS will be determined by a local radiologic assessment using RECIST v1.1. After end of treatment, patients will be followed for survival every 12 weeks (+/- 3 weeks), or more frequently as needed, until death, withdrawal of consent, or the study closes, whichever is the earliest.

Statistical Considerations

Safety Analyses:

Demographic and baseline information (e.g., extent of prior therapy) on study patients will be tabulated. The number of patients studied for the Phase 1 (dose escalation) part of study could range from 12 to 18 evaluable patients, and 22-28 evaluable patients for the Phase 2 (dose expansion) part of the study.

For the Phase 1 part of the study, the following information will be reported for all adverse events observed in the study: dose level, type (organ affected or laboratory determination, such as absolute neutrophil count), severity (by NCI Common Terminology Criteria for Adverse Events (CTCAE) Version 4.03 and most extreme abnormal values for laboratory determinations) and relatedness to study treatment. For each dose the number and percentage of patients experiencing any grade 3, 4, or 5 adverse event will be reported, as well as the number and percentage of patients who experienced selected specific types of adverse events. In addition, the DLTs will be summarized by dose level and the MTD will be determined.

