Although rapamycin, an oral therapeutic, is an efficacious mTOR inhibitor, it has poor solubility, low oral bioavailability, and dose-limiting toxicity (29, 34). Marketed rapamycin analogs are temsirolimus and everolimus. Temsirolimus, approved for the treatment of kidney cancer, is a prodrug of rapamycin and requires conversion by the CYP3A enzyme. Everolimus is approved for pediatric and adult patients with subependymal giant cell astrocytoma, for advanced hormone receptor-positive, HER2-negative breast cancer in combination with exemestane, progressive neuroendocrine tumors of pancreatic origin (PNETs), subependymal giant cell astrocytoma (SEGA) associated with tuberous sclerosis and advanced renal cell carcinoma after failure of treatment with sunitinib or sorafenib (35-39).

Oral rapamycin and currently available rapalogs induce common side effects including hypertension, maculopapular rash (75%), mucositis (50%), asthenia (40%), nausea (43%), thrombocytopenia, metabolic abnormalities and more rarely pneumonitis (8%, 3% grade 3) sometimes fatal (40-42). The most frequently occurring grade 3 or 4 adverse events were hyperglycemia (17%), hypophosphatemia (13%), anemia (9%), and hypertriglyceridemia (6%) (43). These side effects could lead to the discontinuation of the treatment in 60% of patients in some studies.

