4. TABLE OF EVENTS

The schedule of assessments in Table 2 outlines the specific time points for study assessments.

Table 2. Schedule of Assessments

Assessment ^a	Screening ^b (Day -14 to -1)	Cycle 1 through Last Cycle (Treatment Period)			End of Treatment (EOT) Visit ^d	Follow-up Period ^e
		Day 1 ^c	Day 8	Day 15		
General Assessments						
Informed Consent	X					
Demographics	X					
Medical History	X					
Physical Examination	X	X			X	
Vital Signs, Height and Weight	X	X ^f	X ^f	X ^f	X ^f	
BSA Calculation		X ^j				
Prior/Concomitant Medication Evaluation ^g	X	X	X	X	Until 28 days after the last dose of IP	
Prior/Concurrent Procedures Evaluation ^g	X	X	X	X	Until 28 days after the last dose of IP	
ECOG PS	X	X			X	
Pregnancy Test ^h	X				X	
ECG (12 lead) ⁱ	X					
Survival status						X
Adverse Events		Continuous starting from signing of Informed Consent until 28 days after last dose of IP				
Dexamethasone (every cycle)			X			
Nivolumab Dosing		X				
ABI-009 Dosing: To Start after 2nd Nivo dose			X	X		
Local Laboratory Assessments						
Clinical Chemistry Panel	X	X	X	X	X	
CBC, Differential, Platelet Count	X	X	X	X	X	

Assessment ^a	Screening ^b (Day -14 to -1)	Cycle 1 through Last Cycle (Treatment Period)			End of Treatment (EOT) Visit ^d	Follow-up Period ^e
		Day 1 ^c	Day 8	Day 15		
PT, PTT, INR	X					
Urinalysis	X					
Thyroid function	X	X				
HIV, HBV sAg, HBV cAb, HCV Ab	X					
Fasting Lipids	X	X				
Trough rapamycin level ^k						
Immunohistochemistry for PTEN mutation in archived tumor	X					
Imaging and Efficacy Assessments						
CT/MR ^l	X	Every 6 weeks after C1 D1 for the first year, then every 12 weeks thereafter			X	

- a. Unless otherwise specified, visits must occur within \pm 2 days of the planned visit date.
- b. Screening evaluations to be obtained \leq 14 days prior to enrollment unless specified otherwise.
- c. Day 1 evaluations can be omitted if screening evaluations are performed within 72 hours of Cycle 1 Day 1 except for thyroid and fasting lipids every 12 weeks.
- d. End of Treatment Visit must occur at least 4 weeks (\pm 7 days) after the last dose of ABI-009.

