- e. Follow-up for survival and initiation of anticancer therapy can be performed by telephone contact every 12 weeks (+/- 3 weeks) or more frequently if needed, from EOT Visit. All patients that discontinue study drug and have not withdrawn full consent to participate in the study will continue in the follow-up phase for survival and anticancer therapy. This evaluation may be made by record review and/or telephone contact.
- f. Vitals and weight only.
- g. Prior: record all medications taken and procedures done \leq 28 days prior to screening; Concomitant: any medications or procedures after the signing of informed consent.
- h. For females of childbearing potential only. A serum β -hCG pregnancy test must be performed to assess patient eligibility at screening prior to first IP administration (negative results required for IP administration). Urine pregnancy test will be performed at EOT Visit (can be done locally) and as clinically indicated as per institutional guidelines.
- i. ECG to be monitored at screening, and as clinically indicated following standard of care procedures.
- j. Calculated ONLY on C1/D1; to be recalculated only if the weight changes by > 10% in subsequent cycles.
- k. Trough levels of rapamycin will be obtained immediately prior to ABI-009 infusion at Day 15 of the second and third cycles of ABI-009, a week after the first dose in both cycles.
- l. Screening CT/MRI scans must be performed within 28 days prior to study day 1, preferably as close to the day of enrollment as possible. Tumor evaluation by contrast-enhanced CT or MRI of the chest, abdomen, and pelvis will be performed during screening; every 6 weeks (\pm 3 days after C1D1 for the first year then every 12 weeks (\pm 7 days) thereafter until disease progression. EOT visit CT/MRI should be performed only for those patients that discontinue treatment for a reason other than disease progression per RECIST 1.1. If an initial observation of objective response (CR or PR) is made, a confirmation scan should be done at 6 weeks after initial observation.

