5.2.4. Response Assessment

Tumor response will be assessed by CT or MRI scan of the chest, abdomen, and pelvis (CAP); image preparation and evaluation will follow the specifications provided in the RECIST version 1.1. Immune RECIST (irRECIST) will also be obtained. The same modality (CT or MRI) must be used at screening and throughout the study.

CT/MRI scans to be performed at the following frequency:

- ≤2 weeks prior to C1D1 (screening)
- followed by every 6 weeks for the first year; then every 12 weeks until disease progression or unacceptable toxicity. End of Treatment Visit CT/MRI should be performed only for those patients that discontinue treatment for a reason other than disease progression.

An unscheduled scan for suspected disease progression may be performed at any time. However, adherence to the planned imaging schedule is critical regardless of dose delays or unscheduled or missed assessments. Determination of disease progression for clinical management of patients on study will be assessed at the local site. If an initial observation

of objective response (CR or PR) is made, a confirmation scan should be done at 6 weeks after initial observation.

Conditions for Continuation of Treatment in the Presence of Increased Tumor Size by CT scan or MRI Indicating Progressive Disease by RECIST v1.1:

Treatment may be continued if:

1. There are no signs or symptoms indicating unequivocal progression.
2. There is no worsening of ECOG score attributable to progressive disease.
3. There is no tumor growth at critical sites that is life-threatening.
4. Patient signs an informed consent that he/she is aware of alternative therapies but wishes to defer these therapies.
5. There is clinical benefit, as determined by investigator

Table 3. Analyte Listing

Chemistry	Hematology	Coagulation	Urinalysis	Other Labs
Sodium	WBC	PT	Specific gravity	Pregnancy test
Potassium	RBC	PTT	pH	
Bicarbonate	Hemoglobin	INR	Blood	TSH, T3, T4
Chloride	Hematocrit		Protein	HIV
Total protein	MCV		Glucose	HBV sAg
Albumin	MCH		Ketones	HBV cAb
Calcium	MCHC		Microscopic	HCV Ab
Magnesium	RDW			Total Cholesterol
Phosphorus	Platelets			HDL
Glucose	Differential:			LDL
BUN	-Neutrophils			Triglyceride
Creatinine	-Lymphocytes			PD-1\PD-L1
Total bilirubin	-Monocytes			
Alkaline phosphatase	-Eosinophils			
AST (SGOT)	-Basophils			
ALT (SGPT)				
Amylase				
Lipase				

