8.8.3. Other Secondary Efficacy Endpoints

Analysis of other secondary efficacy endpoints PFS at 4 months, RFS at 4 months, median PFS, and median OS will be done separately for the 5 sarcoma subtypes groups. Progression-free survival is defined as the time from the first dose date to the first observation of a disease progression or death due to any cause. If a patient has not progressed or died by the data cutoff date, the PFS time will be censored at the time of the last evaluable tumor assessment.

Recurrence-free survival (RFS) is defined as the time from the first dose date to the first observation of a disease progression or recurrence/progression after surgical resection of tumor, or death due to any cause. If a patient has not progressed or died by the data cutoff date, the RFS time will be censored at the time of the last evaluable tumor assessment.

Overall survival is defined as the time from the first dose date to the date of death due to any cause. If a patient is lost to follow-up before the data cutoff date or still alive by the data cutoff date the OS time will be censored at the last contact date.

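### The plan gives three end points for tumour imaging; under the two shorter ones, patients who stop without progression leave PFS and RFS likely overstated

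*Combined protocol and SAP*

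**What the plan says.** Three places state when imaging ends, and they differ.

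- Synopsis, Overview of Key Efficacy Assessments: "then every 12 weeks thereafter until the end of treatment".
- Section 5.2.4: "then every 12 weeks until disease progression or unacceptable toxicity".
- Table 2 footnote l: 12-weekly scans "thereafter until disease progression".

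The Table 2 grid places the CT/MR entry ("Every 6 weeks after C1 D1 for the first year, then every 12 weeks thereafter") under the treatment period, adds a mark at the end-of-treatment (EOT) visit, and shows nothing under follow-up. Section 5.3 says that participation is complete after the EOT visit. Section 5.4 then collects only survival and later anticancer therapy, by record review or telephone. A patient who stops for a reason other than progression has one scan at the EOT visit, about 4 weeks after the last dose (footnote l, Sections 5.2.4 and 5.3).

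Section 8.8.3 defines PFS as "the time from the first dose date to the first observation of a disease progression or death due to any cause". For a patient with neither event by data cutoff, "the PFS time will be censored at the time of the last evaluable tumor assessment". RFS follows the same rule: "the RFS time will be censored at the time of the last evaluable tumor assessment". No rule covers a stop without progression, new anticancer therapy or a death after missed scans, and no sensitivity analysis is planned for them.

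**The concern.** Staff who follow the synopsis or Section 5.2.4 would stop imaging a patient who leaves treatment for toxicity. Staff who follow footnote l would not. The statement that scans stay on schedule despite dosing delays does not settle this, because it covers delays and not discontinuation.

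Under the shorter readings, follow-up after the EOT scan is lopsided: deaths are still collected but progressions are not. Whether a patient is censored at the EOT scan or counted as a later event then depends on whether that patient dies before cutoff, so the censoring is informative. The PFS rates at 3, 6, 9 and 12 months and the RFS rate at 4 months are exposed. The synopsis rule reaches further than toxicity: it also ends imaging for patients who stop by their own or the investigator's decision, or who complete 18 cycles. Scans that were not taken cannot be recovered at analysis.

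**Working it through.** **What happens to one patient.** Suppose the last dose is at week 12 without progression, the EOT scan at week 16 is clean, and the tumour progresses at week 20.

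- Footnote l: the week-24 scan shows it, so the event is at week 24.
- Synopsis or Section 5.2.4, death 26 weeks after progression: the event is at 20 + 26 = week 46. The patient counts as progression-free at 26 and 39 weeks.
- Synopsis or Section 5.2.4, alive at cutoff: censored at week 16.

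No extra hazard after stopping is needed for this distortion. A late death stands in for an earlier progression.

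**Size.** The plan gives no stop rate, no hazard after stopping and no design figure for PFS, so there is nothing to reproduce and the size can only be illustrated.

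Inputs from the documents: scans 6-weekly in the first year (taken as weeks 6 to 48) and then 12-weekly (from week 60); one EOT scan at 4 weeks; treatment capped at 18 × 3 = 54 weeks; the event and censoring rules of Section 8.8.3.

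Assumptions not in the plan: exponential progression with median 15.3 weeks (the figure that Section 1.1.1 cites for another mTOR inhibitor in sarcoma); median 26 weeks from progression to death; cutoff at 104 weeks; progression hazard after stopping 1, 1.5 or 2 times the hazard before; a share q stopping before progression of 9%, 15% or 30%. The 9% is the nivolumab discontinuation rate for adverse reactions in Section 1.3.3; the other two are chosen values.

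Formulas: progression hazard λ = ln 2 / 15.3 = 0.0453 per week; stopping hazard μ = λq/(1 − q), which is 0.0045, 0.0080 and 0.0194 per week (the 54-week cap brings the realised shares slightly below q). Kaplan-Meier 26-week PFS, simulated with 400,000 patients per row:

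| q | Hazard ratio | Scans to progression | Scans end at EOT, later deaths counted | Difference (points) | Difference if deaths after EOT scan are not counted |
|---|---|---|---|---|---|
| 9% | 1 | 33.7% | 34.8% | +1.1 | −0.3 |
| 9% | 2 | 32.3% | 34.0% | +1.7 | +0.6 |
| 15% | 1 | 33.7% | 35.6% | +1.9 | −0.6 |
| 15% | 2 | 31.3% | 34.3% | +3.0 | +1.0 |
| 30% | 1 | 33.6% | 38.1% | +4.5 | −1.4 |
| 30% | 2 | 28.4% | 34.9% | +6.5 | +1.8 |

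A hazard ratio of 1.5 falls between the rows shown. Median PFS was 18 weeks in every scenario and under every rule.

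The last column shows that most of the difference comes from counting deaths while progressions go unseen. The small negative values arise because a clean off-calendar scan removes patients known to be progression-free from a risk set that still holds undetected progressions.

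**A second set of assumptions.** With toxicity-stop probabilities of 10%, 25% or 40% by week 52 and progression medians of 15.3 or 26 weeks, the overstatement was 0.2 to 3.4 points at 26 weeks and 0.5 to 5.1 points at 52 weeks. The median moved in 1 of 18 scenarios, by one scan interval (24 against 30 weeks).

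**The case against.** The strongest reply is that this is an inconsistency of wording and not a chosen analysis. Section 4 presents Table 2 as the schedule, footnote l carries imaging to progression, and Section 5.2.4 calls adherence to the imaging calendar critical. If footnote l governs, patients who stop for toxicity are scanned on and nothing is censored early. That stands: the documents do not support the inference that toxicity stops will produce informative censoring in this trial whatever is done. They leave it open, and the grid and Sections 5.3 and 5.4 lean towards the shorter reading.

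The effect is also small beside sampling error. With 28 patients and 8 progression-free (29%), the exact 95% interval runs from 13% to 49%. The endpoints are secondary, and Section 8.6 disclaims statistical conclusions. This limits the weight of the point. But a systematic shift is not covered by a confidence interval, and the plan offers these data for planning later trials.

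Three stronger or simpler readings should be resisted.

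- A reader might apply the sentence in Section 1.2.1, "These side effects could lead to the discontinuation of the treatment in 60% of patients in some studies", to this regimen and infer a much larger bias. It describes oral rapamycin and the available rapalogs, not ABI-009 with nivolumab.
- A reader might infer that median PFS is biased. The illustration gives little support for that.
- A reader might infer that there is no bias if stopping leaves the progression hazard unchanged. Under Section 8.8.3 that is wrong, because later deaths count and earlier progressions are unseen.

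**Conclusion.** The conflict between the imaging rules is certain, because it is in the text. Its effect on the analysis is conditional: it arises if the synopsis or Section 5.2.4 is followed, and not if footnote l is. Where it arises, PFS and RFS rates are likely overstated. On the assumptions above, 26-week PFS is too high by about 1 to 2 points if 9% stop before progression, 2 to 3 points if 15% stop and 4.5 to 6.5 points if 30% stop, with the median unchanged. If deaths after the EOT scan were left out, contrary to Section 8.8.3, the difference would be about −1.4 to +2 points. These figures illustrate the mechanism and are not estimates for this trial; RFS was not simulated separately but shares the censoring rule. The primary endpoint (MTD) is unaffected. The point should be corrected, but it does not threaten the trial's main purpose.

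**What to change.** State one imaging end point everywhere: the synopsis, Section 5.2.4, the Table 2 grid and footnote l, and Sections 5.3 and 5.4. Footnote l is the natural base. Scans would continue on the same calendar until progression, death or withdrawal of consent, regardless of treatment discontinuation. The follow-up column of the grid needs a CT/MR entry, Section 5.3 should no longer say that participation ends at the EOT visit, and Section 5.4 should name imaging for patients who have not progressed.

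If scans may stop at new anticancer therapy, which footnote l does not say, Section 8.8.3 needs the matching censoring rule and a sensitivity analysis that counts new therapy as an event. Otherwise the same problem returns by another route. Section 8.8.3 should also say how a death after missed scans is handled.

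The cost is an edit in several sections, plus off-treatment scans for patients who stop without progression, which footnote l already requires.

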Table 5.	Dose Modification Algorithms for Adverse Events Possibly Related to ABI-009	52

LIST OF FIGURES

Figure 1:	Antitumor Activity of ABI-009 in Tumor Xenografts	28
-----------	---	----

LIST OF ABBREVIATIONS AND DEFINITIONS OF TERMS

AE	adverse event
ALP	alkaline phosphatase
ALT	alanine transaminase (SGPT)
ANC	absolute neutrophil count
AST	aspartate transaminase (SGOT)
AUC	area under the time-concentration curve
BSA	body surface area
C _{max}	maximum plasma drug concentration
C _{min}	minimum plasma drug concentration
CBC	complete blood count
CI	confidence interval
CNS	central nervous system
CR	complete response
CS	chondrosarcoma
CT	computed tomography
DMC	data monitoring committee
DNA	deoxyribonucleic acid
DRT	data review team
DOR	duration of response
ECOG PS	Eastern Cooperative Oncology Group performance status
CRF	electronic case report form
EOS	end of study
EOT	end of treatment
GCP	Good Clinical Practice
G-CSF	granulocyte-colony stimulating factor
ICH	International Conference on Harmonisation
IEC	Independent Ethics Committee
IHC	Immunohistochemistry
LPS	liposarcoma

IND	investigational new drug
IP	investigational product
IRB	Institutional Review Board
MedDRA	Medical Dictionary for Regulatory Activities
mg	milligram
mL	milliliter
MRI	magnetic resonance imaging
MTD	maximum-tolerated dose
mTOR	mammalian target of rapamycin
NCI CTCAE	National Cancer Institute Common Terminology Criteria for Adverse Events
ORR	overall response rate
OS	osteosarcoma
OS	overall survival
DCR	disease control rate
PD	progressive disease
PEComa	perivascular epithelioid cell tumors
PFS	Progression-free survival
RFS	Recurrence-free survival
PK	pharmacokinetics
PR	partial response
PTEN	protein tyrosine phosphatase
RECIST	Response Evaluation Criteria in Solid Tumors
SAE	serious adverse event
SD	stable disease
SGOT	serum glutamic oxaloacetic transaminase (AST)
SGPT	serum glutamic pyruvic transaminase (ALT)
TBL	total bilirubin level
ULN	upper limit of normal
UPS	undifferentiated pleomorphic sarcoma

Abbreviation or Term	Definition/Explanation
Study Day 1	First day that protocol-specified IP is administered to the patient.
End of Study	Either the date of the last visit of the last patient to complete the study, or the date of receipt of the last data point from the last patient that is required for primary, secondary, and/or exploratory analysis, as pre-specified in the protocol.
End of Treatment	The date of the last dose of ABI-009 or nivolumab which ever is later for an individual patient.
End of Treatment Visit	For a patient is when safety assessments and procedures are performed after the last treatment, which must occur at least 4 weeks (\pm 7 days) after the last dose of ABI-009 or nivolumab whichever is later.
Primary Analysis	For this study will occur after all patients have either completed the study or completed 12 months of treatment. Patients who are still active at the time of the primary analysis may continue on study until disease progression or medication intolerance is observed.
Follow-up Period	The on-study time period after the End of Treatment Visit. All patients that discontinue study drug and have not withdrawn full consent to participate in the study will continue in the follow-up phase for survival and anticancer therapy. Follow up will continue approximately every 12 weeks (+/- 3 weeks), or more frequently as needed, until death, withdrawal of consent, or the study closes, whichever is the earliest. This evaluation may be made by record review and/or telephone contact.
Efficacy Analysis Dataset	All enrolled patients with measurable tumor per RECIST v1.1 at baseline who received at least two doses of ABI-009 and had a follow-up CT scan/MRI (modified treated population)
Full Analysis Set	All enrolled patients who receive at least one dose of ABI-009 (treated population).
Per-protocol Analysis Set	All enrolled patients who do not have any prospectively defined protocol violations.

Progression-free survival	The time from the first dose date to the first observation of a disease progression or death due to any cause.
Recurrence-free survival	The time from the first dose date to the first observation of disease progression or recurrence/progression after surgical resection, or death due to any cause.
Overall survival	The time from the first dose date to the date of death due to any cause.
Overall response rate	The proportion of patients who achieve a confirmed partial response or complete response per RECIST 1.1. Response rates based on a local radiologic assessment
Duration of response	The time from when criteria of response are first met until the first observation of disease progression per RECIST v1.1 or death due to any cause, whichever comes first.

